**Down-titration period (2 weeks, down-titration by 0.25 mg/day every 2 days):**

- Days 43-44 (start of down-titration period [1.75 mg/day])
- Days 45-46 (1.5 mg/day)
- Days 47-48 (1.25 mg/day)
- Days 49-50 (1 mg/day)
- Days 51-52 (0.75 mg/day)
- Days 53-54 (0.5 mg/day)
- Days 55-56 (0.25 mg/day)

Patients in the placebo arm will follow the same dose escalation, constant dose and down-titration schedule, but will be taking the matching placebo tablets. Patients who have intolerable AEs during the 28-day up-titration period will be allowed to return to the previous tolerated dose at the discretion of the Investigator, or they may withdraw from the study if they so choose.

Each patient is expected to participate in the study for approximately 10 weeks, not including screening. Patients will be treated with IMP for a total of 8 weeks (56 days).

The timing of events is summarized in Table 8.1-1. Study assessments are described in Section 11.

Table 8.1-1 Schedule of events

Study visit number		Visit 1	Visit 2	Visit 3	Visit 4	Visit 5	Visit 6	Visit 7	Visit 8	Visit 9
Study period		Screening	Baseline	Phone Safety Visit	Clinic Safety Visit	Clinic Safety Visit	Clinic Efficacy Visit	Clinic Efficacy Visits	Phone Safety Visit	Follow-up Clinic Visit 
Study day	Protocol Section	Day -28 to Day -5	Day 1	Day 7 ±1 day	Day 14 ±2 days	Day 21 ±2 days	Day 28 ±2 days	Day 42 ±2 days	Day 49 ±2 days	Day 70 ±7 days
Informed Consent	14.3	X								
Eligibility criteria	9.4 & 9.5	X	X 							
Demographics	11.1.3	X								
Vital signs 	11.2.3	X	X		X	X	X	X		X
Physical examination	11.2.2	X								X
Body weight and height 	11.1.4	X								X
Hoehn and Yahr scale 	11.1.8	X	X							
Medical and psychiatric history	11.1.5	X								
Pregnancy test 	11.1.7	X	X							X
12-lead ECG	11.2.4	X	X		X	X	X	X		X
Safety laboratory 	11.2.6	X	X		X	X	X	X		X
MMSE	11.1.9	X								
C-SSRS 	11.2.5	X	X		X	X	X	X		X
UPDRS 	11.3.1	X	X				X	X		X
Diary and wearable device training	11.3.3&11.3.6	X	X							
Randomization	9.9		X							
Study drug dispensing	10.5		X				X	X		
Treatment (Day 1 - Day 56)	10.6					X				

Study visit number		Visit 1	Visit 2	Visit 3	Visit 4	Visit 5	Visit 6	Visit 7	Visit 8	Visit 9
Study period		Screening	Baseline	Phone Safety Visit	Clinic Safety Visit	Clinic Safety Visit	Clinic Efficacy Visit	Clinic Efficacy Visits	Phone Safety Visit	Follow-up Clinic Visit 

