### 9.4 Inclusion criteria

To be eligible to participate in the study, a patient must meet ALL of the following inclusion criteria:

1. Patient is 30 – 85 years old (inclusive) with a diagnosis of idiopathic PD according to the UK Parkinson's Disease Society Brain Bank Clinical Diagnosis criteria.
2. PD patient is stably and optimally treated with L-DOPA; other anti-PD treatments are allowed if used for at least 4 weeks of previous continuous treatment.
3. Patient agrees to be challenged with 150% of their normal L-DOPA dose (maximum L-DOPA dose 250 mg) 30 minutes prior to efficacy assessments at baseline (Visit 2) and at the 2 efficacy clinic visits (Visits 6 and 7).

4. PD patient exhibits troublesome peak-dose LID, confirmed by a score of at least 1 on part IV, item 33 (disability) of the UPDRS at screening (Visit 1) and at Day 1 (baseline, Visit 2).
5. At least 90 minutes in total for each 24-hour period during 2 days are indicated as “ON with troublesome dyskinesia” (according to the PD Home Dyskinesia Diary) prior to Day 1 (baseline, Visit 2).
6. Patient (and/or caregiver) demonstrates ability to accurately complete the PD Home Dyskinesia Diary entries during the screening visit.
7. Patient can read well enough to understand the informed consent document and other subject materials.
8. Female patients of child-bearing potential must have a negative urine pregnancy test at screening (Visit 1) and on Day 1 (Visit 2), must agree to avoid pregnancy during the study, and must practice abstinence (only allowed when this is the preferred and usual lifestyle of the subject) or must agree to use a highly effective method of contraception with a failure rate of < 1% to prevent pregnancy (combined [oestrogen and progestogen containing] hormonal contraception associated with inhibition of ovulation [oral, intravaginal, transdermal], progestogen-only hormonal contraception associated with inhibition of ovulation [oral, injectable, implantable], intrauterine device [IUD] or intrauterine hormone-releasing system [IUS]) starting from 4 weeks prior to administration of the study drug and continuing during the course of the study until 4 weeks after last after IMP administration. Female subjects must agree to refrain from donating eggs from the date of dosing until 3 months after dosing with the IMP. Their male partner must agree to use a condom during the same time frame if he has not undergone vasectomy.

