## 5.5 Definition of baseline

Baseline will be defined as the last non-missing data point prior to the first administration of IMP.

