### **9.2.3      ON Time Without Troublesome Dyskinesia**

Change from baseline in ON Time Without Troublesome Dyskinesia (ON Without Dyskinesia plus ON With Non-troublesome Dyskinesia) based on a PD Home Dyskinesia Diary will be summarized using descriptive statistics for all assessment time points. In this analysis, the number of records of ON Without Dyskinesia plus ON With Non-troublesome Dyskinesia divided by the number of non-missing awake records (sleeping records are excluded) for all measurements prior to Visit 2 and for all measurements from 4\*24 hours prior to and up until Visit 6 and 7 respectively will be used as input data for each patient respectively. If there is not

at least 8 hours recorded data available for each patient and visit window, the corresponding timepoint is set to missing for the patient. ON Time Without Troublesome Dyskinesia will be analysed using inferential statistics as described under 9.2.1 above.

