#### **9.2.6 Dyskinesia measured by a wearable dyskinesia assessment device**

Change from baseline in dyskinesia measured by the Kinesia 360 (Great Lakes Neurotechnologies, Inc) wearable dyskinesia assessment system to Visit 6 (Day 28) and Visit 7 (Day 42) respectively will be summarized using descriptive statistics. In this analysis, the mean of all measurements prior to Visit 2 and the mean of all measurements from 4\*24 hours prior to and up until Visit 6 and 7 respectively for each patient will be used as input data. However, recorded episodes of less than 30 minutes have not been used in the analysis. Furthermore, if there is not at least 8 hours of valid data according to the rules stipulated above for a specific patient and visit, the corresponding timepoint is set to missing for Kinesia 360 data and hence, not used in the analysis. The Kinesia 360 variable “Dyskinesia detect” will be analyzed this way and reported in the CSR. Dyskinesia detect will be analysed using inferential statistics as described under 9.2.1 above.

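### The diary and wearable baselines in SAP 9.2.3 and 9.2.6 have no start limit, while Visits 6 and 7 are capped at 4x24 h; one bounded window should apply at all three visits

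*SAP*

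**What the plan says.** **SAP 9.2.3 (diary).** The endpoint is the count of records in the two favourable ON states, "divided by the number of non-missing awake records (sleeping records are excluded" from the count. The records used are those "for all measurements prior to Visit 2 and for all measurements from" 4x24 h "prior to and up until Visit 6 and 7 respectively will be used as input data for each patient respectively". A timepoint is set to missing unless there is "at least 8 hours recorded data available for each patient and visit window".

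**SAP 9.2.6 (wearable).** The input is "the mean of all measurements prior to Visit 2 and the mean of all measurements from" 4x24 h before Visits 6 and 7. Episodes under 30 minutes are dropped, and 8 hours of valid data are required.

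**Protocol 11.3.3 and 11.3.6.** The diary covers 2x24 h in half-hour intervals, and the wearable a 2-day period, before each of Visits 2, 6 and 7.

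**SAP section 6, Table 2.** The move to 4x24 h is logged and justified for Visits 6 and 7. Nothing is logged for Visit 2.

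**SAP 10.2.3.2, Table ON 1.** The footnote to be printed describes a sum of records over 2x24 h before each visit.

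**SAP 5.5.** "Baseline will be defined as the last non-missing data point prior to the first administration of IMP".

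**Screening.** Protocol Table 8.1-1 places the screening visit between Day -28 and Day -5 and lists "Diary and wearable device training" at Visits 1 and 2. Inclusion criterion 6 requires that the patient or caregiver "demonstrates ability to accurately complete the PD Home Dyskinesia Diary entries during the screening visit".

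**The concern.** A change from baseline should compare like with like. Here the later values come from the four days before the visit, but the baseline can reach back to any record made since screening. The protocol had one window length for all three visits. The SAP lengthened two of them with a reason and left the third open with none. The reason given in Table 2, that 4x24 h is medically acceptable and reduces missing data, supports a 4x24 h limit and not an unlimited one.

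Two things follow. Baseline content can differ from patient to patient in age and origin. The minimum-data rule also loses its force at baseline: eight hours recorded weeks before Day 1 would pass even if nothing came from the scheduled two days.

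The baseline is the value subtracted and also the covariate in the SAP 9.2.1 model. SAP 5.1 and 9.2.1 further plan tests within each arm against its own baseline at the 5% level. Those tests have no control arm to cancel a shift caused by what went into the baseline.

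**Working it through.** The plan gives no effect size, SD or power for these endpoints, so there is no figure to reproduce. The check has three parts.

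**1. Window sizes, at 2 diary records per hour**

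| Window | Calculation | Maximum records |
|---|---|---|
| Protocol, each visit | 2 x 24 x 2 | 96 |
| SAP, Visits 6 and 7 | 4 x 24 x 2 | 192 |
| 8-hour minimum | 8 x 2 | 16 |
| SAP baseline, screened Day -5 | 5 x 24 x 2 | 240 |
| SAP baseline, screened Day -28 | 28 x 24 x 2 | 1344 |

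The last two rows assume continuous recording from screening and no Day 0. They are outer limits, 1.25 and 7 times the 4x24 h window. If only the two planned diaries exist, the baseline holds at most 96 records, half the later maximum.

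**2. Weight of practice records, if any were stored**

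Assume 16 waking hours a day, so two days give 2 x 16 x 2 = 64 awake records. With t practice records the share is t/(64 + t). Assume they differ from the rest by 20 percentage points.

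| t | Share | Baseline shift (points) | Of a 16 h waking day |
|---|---|---|---|
| 2 | 2/66 = 3% | 0.6 | about 6 min |
| 4 | 4/68 = 6% | 1.2 | about 11 min |
| 16 | 16/80 = 20% | 4.0 | about 38 min |
| 32 | 32/96 = 33% | 6.7 | about 64 min |

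The first two rows fit a short demonstration in clinic. The last two need 8 or 16 waking hours of practice recording, which the protocol does not schedule.

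**3. Effect on the tests when the drug does nothing**

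Null simulation with 16:8 patients and 4000 runs. Between arms: ANCOVA of change with baseline as covariate. Within the NLX-112 arm: one-sample t-test. Between-patient SD and day-to-day SD are both assumed to be 0.15 on the proportion scale. Each run has a single post-baseline visit, so this simplifies the planned mixed model.

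| Baseline days / later days | Practice share, shift | Between-arm rejection | Mean within-arm change | Within-arm rejection |
|---|---|---|---|---|
| 2 / 2 | none | 5.0% | -0.001 | 4.7% |
| 2 / 4 | none | 5.4% | 0.000 | 5.0% |
| 14 / 4 | none | 5.1% | 0.001 | 4.6% |
| 2 / 4 | 20%, -0.2 | 5.4% | 0.040 | 22% |
| 2 / 4 | 33%, -0.2 | 5.5% | 0.066 | 48% |

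The Monte Carlo standard error at 5% is √(0.05 x 0.95/4000) = 0.34 points, so every between-arm figure is compatible with 5%.

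The same SDs cover the small shares by direct calculation. The standard error of the mean change in 16 patients is √[(0.15²/2 + 0.15²/4)/16] = 0.0325. Shifts of 0.006 and 0.012 are 0.19 and 0.36 standard errors. With a noncentral t on 15 degrees of freedom, within-arm rejection is about 5.4% and 6.3%. The same formula gives 21% and 48% for the larger shares, in line with the simulation.

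**The case against.** The strongest reply is that the open wording may change nothing. The only recording planned before Visit 2 is two consecutive 24-hour diaries and a 2-day wearable period. If that is all that exists, taking everything before Visit 2 returns the protocol's window. Inclusion criterion 5 also requires two 24-hour diary periods before Day 1, so baseline diaries should be reasonably complete. The 30-minute episode rule would remove very short training wear. The inputs are a proportion and a mean, so window length does not alter the scale. The SAP calls its findings indicative and its tests explorative.

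Most of this stands, and it limits the size of the point. It does not remove the rule itself: whether the open window is harmless depends on data the SAP does not describe, and criterion 5 does not cover the wearable.

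A reader might go further and infer that training entries are in the baseline. The documents do not support that. They schedule training and require a demonstration of ability at screening, but nowhere say that such entries are stored, exported or analysed; nor do they say that they are excluded. A full 24-hour training diary appears nowhere.

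A reader might also infer that the treatment comparison is biased, or that 8 placebo patients make it so. Both arms follow the same rule, and between-arm rejection stayed near 5% even under heavy assumed contamination.

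Nor is SAP 5.5 a serious contradiction. It is a general rule against endpoint-specific derivations, and the protocol pairs the same general rule with a 2x24 h diary. A stated exception is enough.

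**Conclusion.** The defect is in the text and needs no assumption. For both endpoints the baseline window is unbounded and the later windows are capped, contrary to the protocol's equal windows, with no entry in Table 2. The Table ON 1 footnote adds a direct contradiction: a sum over 2x24 h before each visit, against a proportion over different windows in 9.2.3. Two programmers could derive different baselines from this SAP.

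The between-arm comparison is not systematically biased. Unequal window length alone distorted neither test. The exposure is in the within-arm tests of change, and in baseline precision, if early or practice records were kept and differ systematically from the scheduled days. With a brief demonstration the effect is small: 3 to 6% of a two-day baseline, a shift of 0.6 to 1.2 points, and within-arm error of about 5.4 to 6.3%. The 22% and 48% figures need 20 to 33% practice records and show sensitivity only. Waking hours, the 20-point difference and both SDs are assumptions. The point should be corrected because the rule is wrong as written and the repair is cheap.

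**What to change.** - In SAP 9.2.3 and 9.2.6, use one bounded window ending at the visit for Visits 2, 6 and 7: the SAP's own rule of up to 4x24 h.
- Apply the 8-hour minimum inside that window at every visit.
- State that any records from the training visit are excluded, and how they are identified (by date, for example).
- Add the baseline rule and its reason to Table 2.
- Note in 5.5 that these two endpoints are exceptions to the general definition.
- Correct the Table ON 1 footnote to the proportion and window in 9.2.3.
- Keep two sensitivity runs: the all-records baseline, and the protocol's 2x24 h at all three visits.

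The cost is a few sentences, two extra runs per endpoint and no new data. The downside is that a patient whose only pre-baseline records are older than 4x24 h would lose that baseline; the all-records run shows whether this matters.

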#### **9.2.4 Unified Parkinson's Disease Rating Scale (UPDRS)**

Change from baseline in UPDRS combined scores (Parts I, II, III and IV) to Visit 6 (Day 28) and Visit 7 (Day 42) respectively will be summarized using descriptive statistics. UPDRS combined scores will be analysed using inferential statistics as described under 9.2.1 above. The same analysis will be done for UPDRS Part III only.

#### **9.2.5 Clinical Global Impression of Change (CGI-C) in overall PD symptoms**

Change from baseline in CGI-C in overall PD symptoms to Visit 6 (Day 28) and Visit 7 (Day 42) respectively will be summarized using descriptive statistics. In this analysis, rating 0, indicating “no assessment” will be excluded. CGI-C will be analysed using inferential statistics as described under 9.2.1 above.

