Study day	Protocol Section	Day -28 to Day -5	Day 1	Day 7 ±1 day	Day 14 ±2 days	Day 21 ±2 days	Day 28 ±2 days	Day 42 ±2 days	Day 49 ±2 days	Day 70 ±7 days
Diary data collection 	11.3.3		X				X	X		
Wearable device data collection 	11.3.6		X				X	X		
L-DOPA challenge	11.3.1		X				X	X		
UDysRS	11.3.2		X				X	X		
Video taping (UDysRS)	11.3.2		X				X	X		
CGI-S/CGI-C 	11.3.5		X				X	X		
KPPS	11.4.1		X				X	X		
PDQ39	11.4.2		X				X	X		
HADS	11.4.3		X				X	X		
ICIQ-OAB	11.4.4		X				X	X		
ESS	11.4.5		X				X	X		
NLX-112 plasma concentration sampling	11.4.6				X	X	X	X		X
Drug accountability	10.5						X	X		X
Baseline symptoms	11.1.10	X								
Adverse events 	11.2.1						X			
Prior and concomitant medications	11.1.6						X			

CGI-S/CGI-C=Clinical Global Impression of Severity and Clinical Global Impression of Change, C-SSRS=Columbia Suicide Severity Rating Scale, ESS=the Epworth Sleepiness Scale, HADS=the Hospital Anxiety Depression Scale, ICIQ-OAB=the International Consultation on Incontinence Questionnaire Overactive Bladder Module,

KPPS=the King's Parkinson's disease Pain Scale, UPDRS=the Unified Parkinson's Disease Rating Scale, MMSE=Mini Mental Status Exam, PDQ39=the Parkinson's disease Quality of Life Scale (39-item), UDysRS=the Unified Dyskinesia Rating Scale

1. Also early withdrawal follow-up visit
2. Confirmation of eligibility
3. Blood pressure (including orthostatic hypotension assessment), pulse, respiratory rate and temperature. At screening and baseline (Visit 1 and Visit 2), vital signs to assess orthostatic hypotension will be conducted in triplicate, 15-20 minutes apart, with the average of the 3 assessments used for exclusion.
4. Body weight at Visit 1 and Visit 9. Height at Visit 1 only.
5. The Modified Hoehn and Yahr scale will be used to establish the PD stage of the patient.
6. Women of child-bearing potential only.
7. Hematology, coagulation, serum biochemistry and urinalysis.
8. C-SSRS: the baseline scale will be used at the first assessment (screening, Visit 1) and the follow-up scale will be used at all subsequent visits.
9. UPDRS - Screening: part IV only. Other visits: parts I-IV
10. PD Home Dyskinesia Diary: 2 consecutive 24-hour diaries taken prior to the visits indicated above.
11. Wearable data collection will take place during a 2-day period prior to the visits indicated above.
12. CGI-S at baseline (Day 1, Visit 2), CGI-C at other visits.

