#### **11.3.5 *Clinical Global Impression of Severity and Change (CGI-S, CGI-C)***

The CGI-C is a clinician-oriented scale that assesses the total improvement in the patient's condition relative to the clinical global impression of severity (CGI-S) scale conducted at baseline. The CGI-C rates the patient's condition from 0 to 7, with a rating of 0 indicating "no assessment", a rating of 1 indicating "very much better", and a rating of 7 indicating "very much worse".

For timing of assessments, refer to Table 8.1-1.

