### 9.2 Analysis of secondary endpoints

#### 9.2.1 *Statistical inferential analysis of efficacy endpoints*

Absolute change from baseline in efficacy endpoints (secondary and exploratory endpoints) will generally be analysed using a linear mixed model with treatment, visit and the interaction

treatment\*visit as fixed categorical effects and subject within treatment as a random effect. The baseline value of the dependent variable will be included in the model as a continuous covariate, to account for possible differences in change from baseline outcomes due the starting baseline level. Visit will be modelled as a repeated effect. Kenward-Roger's approximation for degrees of freedom will be used.

Providing a significant type III F-test for the interaction effect treatment\*visit, differences between least square estimates of NLX-112 and placebo for the same visit (i.e. from the interaction term treatment\*visit, where visit is the same for both NLX-112 and placebo) will be estimated and the corresponding p-value will be presented in tables. In addition, differences between least square estimates of each post-baseline visit and baseline for NLX -112 and placebo respectively (i.e. from the interaction term treatment\*visit, where treatment is the same for the post-baseline and the baseline visit) will be estimated and the corresponding p-value will be presented in tables.

The model proposed above will be used for FAS and is valid, as long as the underlying data is missing at random (MAR). As a sensitivity analysis, the model will also be run for PPS, serving as a validity check for the main FAS analysis. The sensitivity analysis will be a complete case analysis, i.e., only patients with no missing data for the dependent variable will be used.

Model diagnostics, for example Shapiro-Wilk's test for a normally distributed residual term and Leven's test for the homoscedasticity assumption of the residual term as well as Q-Q plots and plotting residuals vs. predicted values, will be performed. If model assumptions are deemed to be violated, an attempt will be made to transform the dependent variable in order to fulfil model diagnostics.

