A box-cox model will be used to find the most appropriate transformation of data. Lambda values between -3 and 3 will be tested using increments of 0.25. The dependent variable will be transformed accordingly, and the linear mixed model rerun on transformed data. Subsequently, the same model diagnostics as described above will be performed. If model assumptions are deemed to be violated, the linear mixed model approach will not be further pursued for the corresponding dependent variable.

If transforming data according to the above method fails, the analysis will be done using non-parametric methods. A Wilcoxon rank sum test will be used to assess statistically significant differences between active treatment and placebo for relative change from baseline in efficacy endpoints for all post-baseline visits respectively. Furthermore, a Wilcoxon signed rank test will be performed for each post-baseline visit and baseline for NLX -112 and placebo respectively to assess statistically significant differences between each post-baseline visit and baseline for each treatment separately.

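### CGI-C has no baseline value, so the covariate, the within-arm contrasts and both fallback tests of SAP 9.2.1 cannot be run for it, and the general interaction condition withholds its one estimable contrast

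*SAP*

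**What the plan says.** Protocol Table 8.1-1, note 12, fixes which scale is used when: "CGI-S at baseline (Day 1, Visit 2), CGI-C at other visits". Protocol 11.3.5 describes CGI-C as improvement "relative to the clinical global impression of severity (CGI-S) scale conducted at baseline", on ratings from 0 to 7. It defines 0 (no assessment), 1 (best) and 7 (worst).

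SAP 9.2.5 plans a summary of change from baseline in CGI-C at Days 28 and 42, excludes rating 0, and then says "CGI-C will be analysed using inferential statistics as described under 9.2.1 above". It makes no other adaptation.

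SAP 9.2.1 is the general efficacy model. It has treatment, visit and their interaction as fixed effects, and adds: "The baseline value of the dependent variable will be included in the model as a continuous covariate". "Providing a significant type III F-test for the interaction effect", it estimates "differences between least square estimates of NLX-112 and placebo for the same visit". It also plans "differences between least square estimates of each post-baseline visit and baseline for NLX -112 and placebo respectively". If the model and the Box-Cox transformations both fail, a rank-sum test is made "between active treatment and placebo for relative change from baseline in efficacy endpoints for all post-baseline visits respectively", with a signed-rank test of each visit against baseline within each arm.

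The note under SAP Table CG 1 drops the result-category column because CGI-C is a change measure by definition. The shell still has p-value cells b, c and d at both post-baseline visits. The letters are not defined there. In Table UD 1, b and c are the within-arm comparisons with baseline and d is the comparison between arms.

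**The concern.** A general model written for scores measured at baseline and again later is applied to a scale that exists only after baseline. Where 9.2.1 asks for a baseline value of the outcome, CGI-C has none, and 9.2.5 names no substitute. The programmer must leave cells empty or choose a covariate, a reference value and a fallback test that nobody specified in advance.

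The comparison that matters is NLX-112 against placebo, because SAP 5.1 rests any inference of superiority on the between-arm tests. This comparison does not need a baseline CGI-C. It does have to pass the interaction condition in 9.2.1, so naming a covariate would not by itself ensure that it is reported.

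**Working it through.** **1. Match each element of 9.2.1 to the CGI-C data (Visits 6 and 7 only).**

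| Element of SAP 9.2.1 | Needs | Available for CGI-C? |
|---|---|---|
| Outcome | a change score | Yes, if the rating is the change, as the Table CG 1 note says |
| Covariate | baseline CGI-C | No; CGI-S is a different variable and is not named |
| Within-arm visit versus baseline (b, c) | a baseline CGI-C level | No |
| NLX-112 versus placebo at the same visit (d) | ratings at that visit | Yes, subject to the interaction condition |
| Fallback rank-sum on relative change | baseline CGI-C as denominator | No |
| Fallback signed-rank against baseline | baseline CGI-C as pair | No |

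Four elements fail as written. A mock data set of 24 patients × 2 visits = 48 records confirms the covariate problem. With a baseline CGI-C required, 0 of 48 records are usable; without it the model fits, with visit levels 6 and 7 only.

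**2. What the interaction condition tests.** The documents give no power or effect size (SAP 5.2 reports no formal calculation), so there is no stated figure to reproduce. The allocation does reproduce: 24 × 2/3 = 16 and 24/3 = 8.

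With complete data at two visits, the treatment-by-visit F-test equals a two-sample t-test on each patient's Day 42 minus Day 28 difference, with 16 + 8 − 2 = 22 degrees of freedom. It therefore asks whether the effect differs between the two days. If the effect is the same at both, of whatever size, the expected difference is zero and the test is significant with probability alpha = 5% (SAP 5.7).

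**3. Illustration. Assumptions not in the documents: SD 1 at each visit, visit correlation ρ of 0.3, 0.5 or 0.8, no missing data.**

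- Standard error factor: √(1/16 + 1/8) = 0.433.
- Day 42 contrast, effect 1 SD: noncentrality 1/0.433 = 2.31, so power is 59.8% (two-sided 5%, 22 df). A normal approximation gives 63.7%.
- Interaction test: the difference has SD √(2(1 − ρ)), which is 1.18, 1.00 and 0.63 for the three correlations.
- Effect growing from 0.5 SD (Day 28) to 1.0 SD (Day 42): noncentrality 0.5/(SD × 0.433) = 0.98, 1.15 and 1.83, so the condition is met in 15.4%, 19.7% and 41.5% of trials.

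Joint probabilities come from 40,000 simulated trials per scenario, with an unadjusted t-test at Day 42. Ranges run over the three correlations.

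| Effect (Day 28, Day 42) | Condition met | Day 42 significant, no condition | Significant and shown |
|---|---|---|---|
| 1.0, 1.0 SD | about 5% | about 60% | 2.7–2.9% |
| 1.5, 1.5 SD | about 5% | about 91% | 4.0–4.4% |
| 0.5, 1.0 SD | 16–41% | about 60% | 14–29% |

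With scores rounded and clipped to 1–7, the 1.0, 1.0 SD case gives about 57% without the condition and 2.7–2.9% significant and shown. The 0.5, 1.0 SD case gives 13–22% significant and shown. Adjusting for CGI-S (assumed correlation 0.3 with CGI-C; visit correlations 0.4–0.8) gives 58–62% and 2.7–3.2% for the constant 1 SD effect.

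**The case against.** Several counter-arguments have force.

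- **The SAP already treats the rating as the outcome.** This stands. The Table CG 1 note settles it, and the change-from-baseline wording in 9.2.5 is a slip, so the outcome is not among the four failures.
- **CGI-S is the obvious covariate, and 9.2.1 describes only what is generally done.** It is a reasonable choice, and SAP 5.5 might be read as pointing to it. But 9.2.1 asks for the baseline of the dependent variable, and 9.2.5 states no exception apart from dropping rating 0.
- **The interaction condition is not specific to CGI-C.** This also stands. It governs every endpoint sent to 9.2.1, so it should be changed there. The fallback rank-sum test carries no such condition, but it is defined on relative change and so does not help CGI-C.
- **Undefined superscripts are a shell omission.** True: Table KP 1 has the same gap.

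Three stronger readings are tempting but not supported.

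- A reader might infer from Protocol Table 8.2-1, which lists CGI-C in the order of assessments for Visits 2, 6 and 7, that a baseline CGI-C exists. Note 12 of Table 8.1-1 rules that out.
- A reader might infer that b and c would be tested against zero and so be significant whatever happened, since every analysed rating is at least 1. The SAP states no such test.
- A reader might cite the absence of a Visit 2 level in the design matrix as proof of a CGI-C defect. Any change-score endpoint with rows only at Visits 6 and 7 has the same structure. What is particular to CGI-C is that it has no baseline on its own scale.

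**Conclusion.** The point holds. For CGI-C, the baseline covariate, the within-arm comparisons with baseline and both fallback tests cannot be run as SAP 9.2.5 directs. The between-arm contrast is estimable but is reported only when the effect is found to differ between Day 28 and Day 42.

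The 5% rate for an equal effect follows from alpha alone. The drop from about 60% to about 3% rests on an assumed constant 1 SD effect with complete data at 16:8. The loss is smaller if the effect grows between visits.

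The consequence is minor. CGI-C is one of eight listed secondary endpoints, the tests are exploratory and unadjusted (SAP 5.8), and SAP 5.1 calls significant findings indicative. A reader might infer that CGI-C results would be lost. They would not: Table CG 1 gives n, mean, SD and median by arm at each visit regardless. What is withheld or undefined is the inference.

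**What to change.** In SAP 9.2.5:
- Replace change from baseline in CGI-C with the CGI-C rating (1–7, 0 excluded).
- Model it with treatment, visit, treatment-by-visit and baseline CGI-S as the covariate.
- Name a rank-sum test on the raw rating at each visit as the fallback.

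In Table CG 1, delete p-values b and c and define the letters that remain. Testing b and c against a no-change score instead would need a value that the protocol does not define, since it gives meanings only for 0, 1 and 7.

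In SAP 9.2.1, remove the interaction condition so that all endpoints are handled alike. Report the NLX-112 minus placebo difference with confidence interval and p-value at Day 28 and Day 42 whatever the interaction test shows.

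The cost is a few SAP sentences and one table shell before database lock. CGI-S is already collected at Visit 2, so no new data are needed.
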